GCP	Good Clinical Practice
HADS	Hospital Anxiety and Depression Scale
HRQL	Health-related Quality of Life
IB	Investigator's Brochure
IBS	Irritable Bowel Syndrome
IC	Informed Consent
ICC	Intraclass Correlation Coefficient
ICI-RS	International Consultation on Incontinence-Research Society
ICIQ-FLUTS	International Consultation on Incontinence Modular Questionnaire
	for female lower urinary tract symptoms
ICIQ-MLUTS	International Consultation on Incontinence Modular Questionnaire
	for male lower urinary tract symptoms
ICS	International Continence Society
IIEF-5	International Index of Erectile Function 5
IMP IMPD	Investigational Medicinal Product
IPSS	Investigational Medicinal Product Dossier International Prostate Symptom Score
LUTS	Lower Urinary Tract Symptoms
METC	Medical research ethics committee (MREC); in Dutch: medisch
	ethische toetsing commissie (METC)
MUMC+	Maastricht University Medical Centre +
NRS	Numeric Rating Scale
NVOG	C C
OAB	Nederlandse Vereniging Obstetrie & Gynaecologie
OAB-q	Overactive bladder syndrome Overactive Bladder Questionnaire
PRO(M)	
(S)AE	Patient-Reported Outcome (Measure) (Serious) Adverse Event
(5)AE SF-36	Short Form Health Survey 36 (questionnaires)
Sponsor	The sponsor is the party that commissions the organisation or
	performance of the research, for example a pharmaceutical

	company, academic hospital, scientific organisation or investigator. A party that provides funding for a study but does not commission it is not regarded as the sponsor, but referred to as a subsidising party.
SR-BD	Sensation-related bladder diary
SUSAR	Suspected Unexpected Serious Adverse Reaction
VPSS	Visual Prostate Symptom Score
Wbp	Personal Data Protection Act (in Dutch: Wet Bescherming
	Persoonsgevens)
WMO	Medical Research Involving Human Subjects Act (in Dutch: Wet
	Medisch-wetenschappelijk Onderzoek met Mensen)

SUMMARY

Rationale: The overactive bladder syndrome is diagnosed clinically by using the ICS criteria of \geq 8 micturitions and at least 1 urgency episode per 24 hours. To determine whether patients fit the criteria, micturition diaries ('sensation-related bladder diaries') and other symptom questionnaires with considerable limitations are used. This makes it difficult to get a good impression of the fluctuation of complaints during the day / week. These limitations are overcome using the Experience Sampling Method (ESM). This is an electronic questioning method which is characterized by repeated and random, momentary assessments in the subject's current environment and state. This study follows other successful ESM studies done within the Gastroenterology and Psychiatry Department.¹⁻⁴ The aim of this study is to evaluate if the ESM is more accurate in the assessment of urological complaints in OAB compared to the current assessment with the use of the sensations-related bladder diaries (SR-BDs) and retrospective questionnaires. Furthermore the aim is to assess the reliability and validity of this OAB-specific electronic patient-reported outcome measure (ePRO), based on the Experience Sampling Method-principle, for symptom assessment and assessment of triggers for symptoms in OAB.

Objective: To evaluate the accuracy of the ESM to assess urological complaints in OAB compared to SR-BDs and retrospective questionnaires. To assess content validity, reliability and the accuracy to validate the developed ePRO in OAB patients.

Study design: The ESM study is a multi-centre, prospective, cross-sectional study.

Study population: 66 OAB patients will be recruited at the outpatient Pelvic Care Centre at Maastricht UMC+, the outpatient clinic Urology at Zuyderland Heerlen/Sittard and the outpatient clinic Urology at University Hospital Antwerp. 66 healthy volunteers will be recruited as well.

Methods: In a period of 7 days, participants will fill out an electronic ESM assessment at 10 random moments during the day. Moreover, they will fill out a sensation-related bladder diary (SR-BD) during the last three consecutive days of filling out the ESM and several symptom questionnaires at the end of the study period.

Main study endpoints: The main study outcome comprehends the psychometric properties of the PROM for symptom assessment of OAB symptoms. Secondary outcomes are increase in ESM score for OAB symptoms and environmental and psychosocial factors (*e.g.* as measured by the PROM) from one time point (t-1) to the next (t).

Burden, risks and benefits: The burden that is associated with participation in this study comprises completing the PROM questionnaire several times a day, which interrupts daily life due to its random character. Furthermore, the burden is limited to completing a SR-BD and other symptom questionnaires. Most importantly, participating does not bring along

important health related risks. However, awareness could trigger symptoms and therefore be considered as a burden. Nevertheless, for the patients it could be beneficial too to know what triggers complaints, to cope better with their disease.

INTRODUCTION AND RATIONALE

The overactive bladder syndrome (OAB) is defined by the International Continence Society (ICS) as a symptom complex of urgency, usually with frequency and nocturia (awakening at night to void), with (OAB wet) or without (OAB dry) urinary urgency incontinence. Urgency is the complaint of a sudden compelling desire to pass urine, which is difficult to defer⁵. OAB is clinically diagnosed using the ICS criteria of \geq 8 micturitions and at least 1 urgency episode per 24 hours.

It is estimated that approximately 16-17% of the adult population of the Western world is affected by OAB ^{6,7}. The incidence of OAB, both wet and dry increases by age ⁸⁻¹⁰, and because of the worldwide ageing of the population, the number of adults affected by urinary urgency incontinence (UUI) would increase ¹¹. The health care costs of OAB are high ¹², and work productivity can be significantly impacted as well ¹³. In addition, OAB can be associated with comorbidity and increased mortality^{14,15}. Furthermore, OAB with and without incontinence has been associated with significantly lower quality of life scores compared to matched controls without voiding complaints⁸. It is of particular interest that OAB does not only affect the patients, but also has an impact on family members ¹⁰.

There is a strong association between OAB and psychiatric comorbidities such as depression, anxiety and stress ¹⁵⁻¹⁹. This association is most likely bidirectional.^{16,18,19} The current methods of diagnosis rely on voiding diaries (the sensation-related bladder diary) and retrospective questionnaires.

Retrospective, self-reported outcomes have important limitations. Firstly, there is a high risk for recall bias, in which retrospective information consists of a reconstruction of a few specific moments rather than a reliable reflection of symptoms over a predefined period of time²⁰⁻²². Furthermore, it is well described that memory retrieval is influenced by the individual's environment and mental state at the time of recall, known as ecological bias.^{20,21} In conclusion, patient experiences about symptoms in the past can be significantly distorted when retrospectively reported. Furthermore, lack of patient compliance is an important disturbing factor in recalled assessments. Studies that employed paper diaries in a population of patients with chronic somatic pain to measure symptoms resulted in very low patient compliance: only 11% actual compliance, but up to 80% fake compliance was determined, the latter presumably resulting from filling in diaries after the proscribed time window.²³

The Experience Sampling Method (ESM), also referred to as Ecological Momentary Assessment (EMA), may overcome these limitations. ESM is an electronic questioning method characterized by random, repeated assessments in the subject's current state and environment, for several consecutive days. A digital device sends out an auditory beep at random moments during the day, to which subjects have to respond by completing several assessments at the device. The assessments are identical between the moments ^{20,21,24}. Hereby, ESM offers the opportunity to reduce the risk for recall bias and to capture symptom variability over time with taking into account contextual, social and psychological factors, which might have an impact on symptom reporting.

ESM has already been used in different patient populations with different disorders, such as; irritable bowel syndrome (IBS) ¹, depression ^{25,26}, Parkinson's Disease ²⁷ and mental illness in a broad sense.²⁸

ESM has proven to be a viable and novel approach to assess symptoms, affective states and contextual factors at the level of the individual subject²⁷. It provides precise, prospective information that may contribute to clinical practice²⁶ with several distinct advantages over traditionally used (retrospective) assessment of mental health related phenomena²⁸. OAB shows fluctuating symptom patterns in which urological complaints might be influenced by daily life factors as well as psychological and psychiatric comorbidities. To our knowledge, there are no previous studies on the use of ESM in a urological patient population. In order to study the performance of ESM in a population as such there is a need for developing a patient-reported outcome measure suitable for real-time symptom assessment of urological symptoms, using the ESM principle. Patient-reported outcome measures (PROMs) are assessment methods completed by patients, and are meant to capture one or several aspects of a disease course or health status²⁹. Focus group research in OAB patients was done for item selection and to evaluate the quality of the PROMs according to the ESM principle. The outcomes of the focus groups have been discussed in an expert meeting and a final questionnaire has been constructed, specifically for the ESM in the urological patient population. Now, this OAB-specific ESM tool should be tested to see if there is a difference between symptom scores on ESM and the currently used retrospective reports and SR-BDs. Furthermore content validity, reliability and the accuracy will be tested to validate the developed ePRO in OAB patients. Additionally, specific triggers for the onset of OAB complaints will be objectified, with use of the OAB specific ESM tool. It will be objectified if there is a direct link between OAB and psychiatric disorders as depression, anxiety and stress too.

Summarizing, electronic, repeated symptom assessments during daily activities should assure ecological validity and eliminate recall bias, lead to higher compliance rates, and capture symptom variability during the day. For these reasons it is expected that the Experience Sampling Method (ESM) may prove to be a more objective tool for evaluation and quantification of urgency and other urological complaints that will overcome the limitations of currently used retrospective symptom assessment methods in OAB.

1. OBJECTIVES

This project will be subdivided into three sections:

Part I. Comparison of the ESM vs. SR-BDs and other retrospective questionnaires in the assessment of urological complaints in OAB such as urgency.

Part II. Validation of new patient-reported outcome measure, based on the Experience Sampling Method, which will be used in the assessment of urological symptoms in patients with overactive bladder syndrome.

Part I – Comparison of assessment methods

Primary aim: To compare the ESM to SR-BDs and other retrospective questionnaires in the assessment of urological complaints in OAB.

Objectives:

1. To compare the ESM to SR-BDs and other retrospective questionnaires in the assessment of urological complaints in OAB.

Hypothesis: The ESM is more accurate in the assessment of urological complaints in OAB compared to the current use of SR-BDs and other retrospective questionnaires (like the OAB-q). We hypothesize to find good correlations between ESM scores (i.e. the newly developed ePRO) and 'concurrent' instruments (i.e. conventional retrospective questionnaires), since we purport to measure the same constructs with both methods. However, ESM measures real-time symptoms whereas our conventional questionnaires measure retrospectively. Therefore, we do not expect to find perfect correlation coefficients, i.e. >0.8. Correlation coefficients between 0.4 and 0.8 are considered appropriate. Correlation coefficients lower than 0.4 reflect very weak or no correlation between the methods, which probably means that we are measuring some other construct with our new ePRO than is measured with the conventional method (current 'gold standard'). On the contrary, correlation coefficients higher than 0.8 reflect very strong correlations, meaning that we are more or less measuring exactly the same construct. In this case, there is no rational for replacing the conventional methods by the new (more intensive) method. For each correlation coefficient its significance will be checked as well.

Furthermore it is expected that the mean urgency scores from the ESM will be significantly lower when compared to the urgency scores from the SR-BDs and retrospective questionnaires.

Additionally it is expected that in the SR-BDs the daily peak of urgency scores is reported rather than the average level of urgency over the day.

Part II - Validation

Primary aim: To validate and test the reliability of electronic patient-reported outcome (ePRO) for the evaluation of the complex symptoms and their potential triggers in OAB patients in day-to-day life with the use of the Experience Sampling Method.

Objectives:

1. To assess content validity of the developed ePRO.

Hypothesis: We consider content validity of the ePRO adequate since items were carefully selected based on evidence from qualitative studies. Furthermore, item relevance was judged by a multidisciplinary panel of experts in the fields of urology, gastro-enterology, psychiatry and gynaecology as well as by OAB patients.

2. To assess concurrent validity of the developed ePRO.

Hypothesis: We hypothesize to find good correlations between ESM scores (*i.e.* the newly developed ePRO) and 'concurrent' instruments (*i.e.* conventional retrospective questionnaires), since we purport to measure the same constructs with both methods. However, ESM measures real-time symptoms whereas our conventional questionnaires measure retrospectively. Therefore, we do not expect to find perfect correlation coefficients, *i.e.* >0.8. Correlation coefficients between 0.4 and 0.8 are considered appropriate. Correlation coefficients lower than 0.4 reflect very weak or no correlation between the methods, which probably means that we are measuring some other construct with our new ePRO than is measured with the conventional method (current 'gold standard'). On the contrary, correlation coefficients higher than 0.8 reflect very strong correlations, meaning that we are more or less measuring exactly the same construct. In this case, there is no rational for replacing the conventional methods by the new (more intensive) method. For each correlation coefficient its significance will be checked as well.

3. To assess internal consistency of the developed ePRO.

Hypothesis: We hypothesize that internal consistency of the ePRO will be moderate to good, since items were based on theoretical constructs as described in literature. Therefore, we expect to find correlation coefficients (Cronbach's α) of >0.6.

4. To assess test-retest reliability of the developed ePRO.

Hypothesis: Since OAB symptoms might fluctuate within the study period, we do not expect to find perfect test-retest reliability (i.e. test-retest reliability coefficients close to 1.00). However, it is hypothesized that symptoms will show certain subject-specific patterns, so consistency between the first half-week and the second-half week is expected. Therefore, we hypothesize to find test-retest reliability coefficients around 0.70-0.80.

5. To assess how well the developed ePRO differentiates between OAB and healthy subjects, by determining the accuracy of the discriminatory model using a confusion matrix.

Hypothesis: We hypothesize that the accuracy of the ePRO to differentiate between OAB and healthy subjects will be comparable with ICS criteria, i.e. moderately to good. There are no studies that examined the sensitivity or specificity of these criteria. However, since OAB-like symptoms often occur in healthy subjects we expect that the ePRO might classify some healthy subjects as OAB (i.e. false positives) resulting in moderate sensitivity and high specificity.

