6. STATISTICAL ANALYSIS

Part I – Comparison of the ESM to SR-BDs and other retrospective questionnaires

In case of incomplete ESM data, we will not use imputation techniques as these techniques have similar assumptions on the mechanisms of missing data as the statistical model described in the remaining text.

Experience Sampling Methods produce complex multilevel data structures, and analysis techniques need to take the variation between subjects and repeated measures within subjects into account. Associations between urological symptom scores of the SR-BD and corresponding ESM scores will be tested using linear mixed-effects models, with a random intercept to account for clustering of measurements within patients, and an autoregressive (AR1) covariate structure to account for correlations of measurements over time. Currently the SR-BD can be seen as the standard method and will therefore be used as dependent variable in the analysis. For each participant, ESM day-mean scores of individual symptoms will be used as predictor, to test whether average symptom scores of the day reflect the day-mean SR-BD scores.

To quantify the difference of scores between the two methods, ESM data will be subtracted from corresponding day-mean SR-BD scores, resulting in a delta score, which will be statistically tested using the same multilevel analysis, adjusting for repeated measures. In like manner, the differences between the mean SR-BD scores and ESM maximum scores of the day will be tested.

To investigate if certain patient characteristics lead to a different retrospective perception of urgency, possible predictors of a larger delta-score (i.e. the differences in urgency reporting between ESM day-mean scores and the day-mean SR-BD scores) will be tested: i.e. gender, age, presence of comorbid panic disorder and psychological symptoms (HADS).

Part II Validation

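### The Summary aim and the Part I hypothesis claim that ESM is more accurate, but the planned comparisons can show only association and difference between self-reports

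*Combined protocol and SAP*

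**What the plan says.** **The claim.** The Rationale paragraph of the Summary states: "The aim of this study is to evaluate if the ESM is more accurate in the assessment of urological complaints in OAB", with SR-BDs and retrospective questionnaires as the comparators. The Objective paragraph of the Summary also speaks of accuracy relative to those methods. In Section 1, Part I, the hypothesis under the only objective is: "The ESM is more accurate in the assessment of urological complaints in OAB compared to the current use of SR-BDs and other retrospective questionnaires".

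**The labelled aim.** The heading line of Part I is neutral: "Primary aim: To compare the ESM to SR-BDs and other retrospective questionnaires in the assessment of urological complaints in OAB".

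**How results are to be read.** Section 1 gives two expectations. On correlation: "Correlation coefficients between 0.4 and 0.8 are considered appropriate". A coefficient below 0.4 suggests a different construct, and one above 0.8 leaves no reason to replace the conventional methods. On level, it expects that "mean urgency scores from the ESM will be significantly lower when compared to the urgency scores from the SR-BDs and retrospective questionnaires". No result is tied to ESM being more accurate, or to its not being so.

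**The analyses.** Section 6, Part I, plans:
- a mixed model with the SR-BD as outcome and the ESM day-mean as predictor, because "Currently the SR-BD can be seen as the standard method and will therefore be used as dependent variable in the analysis"
- a difference analysis in which "ESM data will be subtracted from corresponding day-mean SR-BD scores, resulting in a delta score"
- the same difference using the ESM maximum of the day
- a search for predictors of a larger delta (gender, age, panic disorder, HADS)

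Section 6.1, under the Part II heading, adds concurrent-validity models against the SR-BD and questionnaires, and paired t-tests of ESM subject means against questionnaire scores.

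**The concern.** Accuracy means closeness to a true value. To rank two methods on accuracy, a plan needs a reference that is neither of them, or explicit assumptions about their errors that make the ranking estimable. This plan has neither for urgency or the other symptoms. It names the SR-BD as the standard method and, in Section 1, calls the conventional method the current gold standard. If that is taken literally, every departure of ESM from the SR-BD counts as ESM error, and ESM could at best equal it. If it is not, a difference shows that the two disagree and does not show which is off.

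What is at stake is the conclusion the study may draw. Section 8.6 commits to peer-reviewed publication. If the expected results appear (moderate correlation, lower ESM mean), the present wording leaves room to report them as support for superior accuracy, although the opposite ranking could produce the same statistics.

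**Working it through.** The plan gives no figure for accuracy, so there is nothing to reproduce. The check has three steps.

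**1. What each analysis uses.**

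| Analysis | Place | Inputs | Reference outside the self-reports? |
|---|---|---|---|
| SR-BD regressed on ESM day-mean | 6, Part I | SR-BD, ESM | No |
| Delta, SR-BD day-mean minus ESM | 6, Part I; 6.1 | SR-BD, ESM | No |
| Delta with ESM daily maximum | 6, Part I; 6.1 | SR-BD, ESM | No |
| Predictors of delta | 6, Part I; 6.2 | SR-BD, ESM, patient characteristics | No |
| Concurrent validity | 6.1 | ESM, SR-BD, questionnaires | No |
| Paired t-tests | 6.1 | ESM subject mean, questionnaires | No |

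**2. Can the same results arise under opposite accuracy rankings?** The documents give no SDs, so these values are assumed: both scores on one scale with SD s = 2, correlation r = 0.60, and SR-BD mean d = 1 point above the ESM mean. One level of data is used for simplicity.

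- Covariance: r × s² = 0.60 × 4 = 2.4
- Slope of SR-BD on ESM: 2.4 / 4 = 0.60
- Mean delta: 1.00
- SD of delta: √(4 + 4 − 2 × 2.4) = √3.2 = 1.79

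None of these depends on which score is called the truth. The root mean square error (RMSE) of the other method is √(3.2 + 1²) = √4.2 = 2.05.

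| | r | Slope | Mean delta | SD of delta | RMSE, ESM | RMSE, SR-BD |
|---|---|---|---|---|---|---|
| ESM equals the truth | 0.60 | 0.60 | 1.00 | 1.79 | 0 | 2.05 |
| SR-BD equals the truth | 0.60 | 0.60 | 1.00 | 1.79 | 2.05 | 0 |

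A simulation of 1,000,000 draws gave the same values. Both rows fall within the 0.4 to 0.8 band and both show the expected lower ESM mean.

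The result is the same across the plan's own band. The SD of delta is s√(2(1 − r)) and the RMSE of the erring method is √(2s²(1 − r) + d²):
- r = 0.4: SD of delta √4.8 = 2.19; RMSE √5.8 = 2.41
- r = 0.8: SD of delta √1.6 = 1.26; RMSE √2.6 = 1.61

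In each case the RMSE moves from one method to the other while the observable statistics stay put. Random intercepts, AR(1) errors, daily maxima and patient-level predictors do not alter this. They are computed from the same observed scores and characteristics, and no observed variable marks the truth.

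**3. Do the two methods score the same moments?** Section 4.2 triggers ESM at 10 random times between 07:00 and 22:00. Section 4.2.3 has the SR-BD filled in after each micturition. If urgency tends to be higher around a void than at a random moment (an assumption), the SR-BD mean will exceed the ESM mean even when both are perfectly accurate. The expected direction of delta therefore needs no error in either method.

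**The case against.** **The primary aim is only to compare.** This is correct. A reader might infer that the primary aim is superiority, or that the first objective cannot be answered. The documents do not support that: both the Part I aim and its objective are worded as a comparison, and the planned analyses do compare the methods. What cannot be tested is the hypothesis sentence and the Summary aim.

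**The maximum-score and delta-predictor analyses probe mechanism.** They address peak reporting and distorted recall, which the Introduction and Section 1 put forward as the reasons to expect ESM to do better. They are informative about where the methods part company. They remain functions of the same difference, however, and reading that difference as recall bias presumes that ESM is true. Section 4.1.1 gives the SR-BD a recall of only several minutes, which weakens that presumption for the main comparator.

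**Some error models would make the ranking estimable.** A reader might infer that the planned statistics can never separate the methods. That goes too far. With true scores on the same scale and independent errors, the slope of SR-BD on ESM would estimate ESM reliability. The plan states no such model, and the different sampling moments make identical true scores hard to assume.

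**Part II supplies other evidence.** Half-week test-retest covers ESM only and cannot detect systematic bias. Objective 5 classifies OAB against healthy subjects from the ePRO alone. Running the same classification for the diary would not close the gap either. It would measure group discrimination rather than accuracy of urgency scores, against a diagnosis partly based on diaries (Summary; Section 3.1) and with controls who have no diagnosis of lower urinary tract symptoms (Section 3.3.2).

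**No rule says the results will be read as superior accuracy.** This is true, and a reader should not infer that the plan commits to that reading. But no rule prevents it, and the hypothesis as worded invites it.

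**Conclusion.** The point holds for the Summary aim and the Part I hypothesis: the accuracy claim is not testable by the planned comparisons, which use only the self-reports being compared. In the illustration, identical correlation, slope and delta go with an RMSE of 0 for one method and 2.05 for the other, in either order. The scale of those numbers depends on the assumed SD of 2 and 1-point difference. The conclusion needs only that no outside reference is observed and that no error model is specified to replace one. Data collection and the comparison itself stand; what changes is what the study may conclude.

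**What to change.** 1. In the Summary (Rationale and Objective) and in the hypothesis under Part I, objective 1, replace the accuracy claim with one of association and difference. For example: *ESM urgency scores correlate with, and are on average lower than, urgency scores from the SR-BD and the retrospective questionnaires.*
2. Add to Section 1 or Section 6, Part I: *Neither a lower ESM mean nor a correlation between 0.4 and 0.8 will be interpreted as showing that ESM is more accurate.*

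No new data, analysis or sample size is needed. The cost is a text amendment and a more modest stated claim.
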